4.3.3 End of Treatment (EOT) Visit

The following assessments will be performed for subjects who do not experience treatment failure at any time during the Treatment Phase:

- Assess for any Adverse Events and changes in Concomitant medications (see [section 9](#) and [7.5](#)),
- Complete Physical Examination (see [section 7.7](#)),
- Vital Signs (see [section 7.10](#)),
- Neurological Assessment (see [section 7.9](#)),
- Subject-perceived Injection Site Pain Assessment (see [section 7.14](#)),
- Collection of Blood Specimens (see [section 7.11](#)) for
 - Plasma HIV-1 RNA level
 - TruCount T Assay
 - Complete Blood Count
 - Biochemistry
 - Anti-idiotypic antibodies to PRO 140
 - PK sample for PRO 140
 - Serum Conc. of ART Drugs

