- $<1 \log_{10}$ copies/mL decrease in HIV-1 RNA at or after Week 4 of Treatment Period Part 2 unless HIV-1 RNA <400 copies/mL. *[Assessment Timepoint: from T6 up to T25 visit]*
- Confirmed plasma HIV-1 RNA levels ≥ 400 copies/mL at Week 25 of the Treatment Period *[Assessment Timepoint: T25 visit]*

b) Virologic rebound is defined as two consecutive viral load results of:

$\geq 1.0 \log_{10}$ copies/mL increase in plasma HIV-1 RNA above nadir level* in Treatment Period Part 2 *[Assessment Timepoint: from T3 up to T25 visit]* or

*Note: This refers to “Nadir” level in the Treatment Phase which starts from T2 visit

- ≥ 400 copies/mL after suppression to <50 copies/mL in Treatment Period Part 2. *[Assessment Timepoint: from T3 up to T25 visit]*

(4) **Follow-Up Phase:** The duration of follow-up depends on whether or not subject has experienced treatment failure during Treatment Period Part 2.

- Subjects who experience treatment failure within Treatment Period Part 2 will be followed up every 4 weeks until viral suppression is achieved (i.e., plasma HIV-1 RNA levels below level of detection) or up to a maximum of 6 months after cessation of therapy if the treating physician does not feel that there is an antiretroviral regimen that will regain full viral suppression.

- Subjects who do not experience treatment failure at the end of Treatment Period Part 2, will be followed up every 2 weeks for total of 4 weeks.

Procedures to be performed during each of these study phases are described below and provided as a Schedule of Assessments in [Table 4-1](#) and [Table 4-2](#).

Table 4-1: Schedule of Assessments – Screening and Treatment Phase

Procedure/Assessments	Screening Visit	Treatment Phase (26 weeks)																In case of Treatment Failure			
		ART only (1 week)	IP + ART (1 week)		IP + OBT (24 weeks)																
Visit	SV	T0	T1		T2	T3	T4-6	T7	T8 - 10		T11	T12-14	T15	T16-18		T19	T20-22	T23	T24-25	EOT	TF
			(Pre-Rx)	(Post-Rx)					1 week ±3 days since last treatment	1 week ±3 days since last treatment				1 week ±3 days since last treatment	1 week ±3 days since last treatment						
Window Period		Within 6 weeks of the Screening visit	Within 1 week ±3 days since T0		1 week ±3 days since last treatment																
Informed Consent ^[1]	X																				
Eligibility Evaluation ^[2]	X																				
Subject Demographics	X																				
Medical History ^[3]	X		X																		
HIV History	X		X																		

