- Anytime during the Treatment Phase, if treatment failure occurs or have met any other criteria for discontinuation of study treatment as specified in [section 5.2.1](#) of the protocol. Subjects

will be allowed to continue PRO 140 with existing OBT regimen while waiting for new regimen to be constructed by the Investigator.

Note:

- Subjects may return to clinic for an additional blood draw in-between the clinic visits for plasma HIV-1 RNA levels, per the discretion of the Investigator.
- Subjects who experience treatment failure at any time during the Treatment Phase will undergo the Treatment Failure (TF) Visit assessments and enter the Follow-up Phase of the study.
- Subjects who meet any criteria (other than treatment failure) for discontinuation of study treatment as specified in [section 5.2.1](#) of the protocol, will undergo End of Treatment Phase (EOT) Visit assessments and enter the Follow-up Phase of the study.
- Subjects who do not experience treatment failure will enter the Follow-up Phase of the study at the end of 25-week Treatment Phase.

Visits during the Treatment Phase will commence on T1, i.e. the date of first treatment, with weekly visits (\pm 3 days) thereafter. The first Treatment Visit (T1) will take place as soon as HIV-1 viral tropism, genotypic and/or phenotypic resistance results are available for review by Investigator, within 6 weeks of the Screening Visit.

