8.2.2 Secondary Endpoint

The secondary endpoints will be as follows:

1. Proportion of participants with $\geq 1 \log_{10}$ reduction in HIV-1 RNA viral load from baseline to the end of the initial 1-week treatment period
2. Mean change from Baseline in HIV-1 RNA levels (\log_{10} copies/mL) to the end of the initial 1-week treatment period
3. Percentage of participants achieving HIV-1 RNA < 400 copies/mL at week 25
4. Percentage of participants achieving HIV-1 RNA < 50 copies/mL at week 25
5. Mean change from Baseline in HIV-1 RNA levels (\log_{10} copies/mL) at week 25
6. Mean change from Baseline in CD4 cell count at the end of the initial 1-week treatment period
7. Mean change from Baseline in CD4 cell count at week 25

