8.3 SAMPLE SIZE DETERMINATION AND RATIONALE

Up to 25 subjects (or any number of subjects that can be enrolled by the time of BLA submission for PRO 140) will be enrolled in this study. The sample size is based on clinical judgement with an intention to supplement the data for the target BLA indication.

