8.6.4 Handling of Missing Data

For the per protocol analysis of efficacy endpoints there will be no imputation of missing data. However, missing data will be imputed using different methods that will be detailed in the SAP for the ITT population of the primary and secondary endpoints.

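### The four week-25 endpoints depend on an EOT visit that routes out treatment failures and has no fixed week for other early stoppers, so the unimputed per-protocol result is selected on outcome and overstates response

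*Protocol*

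**What the plan says.** Section 8.2.2 lists four secondary endpoints at week 25: RNA below 400 ("Percentage of participants achieving HIV-1 RNA < 400 copies/mL at week 25"), RNA below 50, mean change in log10 RNA and mean change in CD4 count.

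Table 4-1 and sections 4.3.2 and 7.11.7 place RNA and TruCount at T1, T2, T3, T7, T11, T15, T19 and T23, then at EOT or TF. Nothing is drawn at T24 or T25.

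Who has which visit is set in three places:

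- Section 4.3.3, on EOT: "The following assessments will be performed for subjects who do not experience treatment failure at any time during the Treatment Phase".
- Sections 4.3 and 4.3.4: a subject who fails has a TF visit at that time and a change of background therapy. Table 4-2(b) then times visits from TF. Under section 5.1 such a subject has completed the study once suppressed, or after at most 6 months.
- Section 4.3, on subjects who stop for any reason other than failure: they "will undergo End of Treatment Phase (EOT) Visit assessments and enter the Follow-up Phase of the study", with no week attached.

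Confirmed RNA of 400 or more at the end of Part 2 is itself a failure criterion, assessed at T25.

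On analysis, the synopsis makes ITT primary for both primary and secondary endpoints. Section 8.7.4.2 makes PP supportive, to check consistency, with the same methods apart from the population. Section 8.6.4 says: "For the per protocol analysis of efficacy endpoints there will be no imputation of missing data". For ITT it promises imputation, with methods left to the SAP.

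**The concern.** Whether a subject has a week-25 value depends on how that subject responded. Failures leave the EOT stream, and one route out uses the same 400-copy cut-off as the endpoint. Early stoppers stay in the stream, but under a visit label that does not say when the sample was taken.

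The primary endpoint is at week 1, so evidence for the other part of the primary objective, efficacy with optimized background therapy over 24 weeks, comes from these secondary endpoints. They are meant to support a licence application: "The sample size is based on clinical judgement with an intention to supplement the data for the target BLA indication". A PP table that omits failures cannot check the consistency of an ITT table that includes them. Observed mean changes in RNA and CD4 would describe non-failures without saying so.

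**Working it through.** The protocol has no sample-size or power calculation for these endpoints ("Up to 25 subjects (or any number of subjects that can be enrolled by the time of BLA submission for PRO 140" enrolled), so there is no plan figure to reproduce. The check is of the timeline and the denominators.

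**Timeline.** With weekly visits, T_k falls k − 1 weeks after T1. T23 is week 22, T25 is week 24, and EOT one week later is week 25. EOT is therefore the only scheduled week-25 sample.

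**Failures.** A subject who fails at T7 (week 6) and is suppressed at TF-FU1 (6 + 4 = week 10) has completed the study with no week-25 sample. A later failure may happen to have a follow-up sample near week 25, but after the change of background therapy. Section 5.2.2 asks that subjects who stop treatment be followed per protocol; for failures that is this same schedule.

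**Other early stoppers.** A subject who stops at week 5 has EOT at week 5 and a last visit at 5 + 4 = week 9.

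**Non-responder rule.** The only one stated (synopsis and section 8.6.1.1) covers subjects who leave before their first post-baseline assessment. It does not reach later failures or stoppers.

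**Simple illustration.** Assume N = 25, 5 failures before week 25, and all others below 400:

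- Observed: 20/20 = 100% (exact 95% CI 83.2 to 100).
- All treated, failures as non-responders: 20/25 = 80.0% (59.3 to 93.2).

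**Range.** Each assumed split of 25 is given as: below 400 at week 25 / failed earlier / confirmed 400 or more at week 25 / stopped early with EOT below 400 / stopped early with EOT 400 or more. Reading A follows sections 4.3.3 and 4.3.4 literally, so a confirmed week-25 failure has no EOT value. Reading B lets the EOT sample be the first of the two results, so that subject keeps an EOT value.

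| Split | A, completers | A, early EOT pooled | B, completers | B, early EOT pooled | All treated |
|---|---|---|---|---|---|
| 20/2/1/1/1 | 20/20 = 100% | 21/22 = 95.5% | 20/21 = 95.2% | 21/23 = 91.3% | 20/25 = 80.0% |
| 16/4/2/1/2 | 16/16 = 100% | 17/19 = 89.5% | 16/18 = 88.9% | 17/21 = 81.0% | 16/25 = 64.0% |
| 12/7/3/1/2 | 12/12 = 100% | 13/15 = 86.7% | 12/15 = 80.0% | 13/18 = 72.2% | 12/25 = 48.0% |
| 10/10/3/1/1 | 10/10 = 100% | 11/12 = 91.7% | 10/13 = 76.9% | 11/15 = 73.3% | 10/25 = 40.0% |

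Every observed-case figure exceeds the all-treated figure, by between 91.3 − 80.0 = 11.3 and 100 − 40 = 60 points. Under A, unconfirmed single values of 400 or more in an assumed 2% to 10% of completers would lower 100% to 98% to 90%.

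**Mean change.** With an assumed −3.0 log10 in non-failures and −0.3 in 5 failures, the observed mean is −3.0. Over all treated it is (20 × −3.0 + 5 × −0.3)/25 = −2.46.

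**Visit timing.** The treatment window is "1 week ±3 days since last treatment", so deviations accumulate. If it also governs EOT, T1 to EOT spans 25 intervals, nominally 25 × 7 = 175 days. A steady 1-day shift gives 150 to 200. The outer limits, 25 × 4 = 100 and 25 × 10 = 250, need every interval at its limit in one direction.

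**Wording of the 400-copy criterion.** The synopsis places it at week 25 of Part 2, section 4 at week 25 of the treatment period, and sections 4.3.4 and 5.2.1 at week 24 of Part 2. All name T25. The same lists pair day 7 of Part 2 with T3 and week 4 with T6, so Part 2 counts from T2. T25 is then week 23 of Part 2, and no RNA is scheduled there.

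**The case against.** The strongest reply is that ITT is the main analysis of these endpoints and that section 8.6.4 leaves its imputation to the SAP, which may well count failures and discontinuers as non-responders. This stands. A reader might infer that the main week-25 result is biased; the protocol does not support that.

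A second reply is that barring imputation does not oblige anyone to drop failures. PP keeps every treated subject without a major violation, and scoring a documented failure as a non-responder is an endpoint rule, not imputation. That is possible, but the protocol states no such rule. Its endpoint is an RNA level "copies/mL at week 25", and a failure has no sample scheduled then. Read plainly, the value is missing and stays missing.

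A reader might also infer that RNA below 400 is assured by design. That holds, or nearly so, only for 25-week completers under reading A. Because no RNA is scheduled at T25, the EOT sample may itself be the first of the two results, and then some values of 400 or more remain. For the same reason it is too strong to say that a failure can never have an EOT value. Early stoppers may be above 400 as well. RNA below 50 is selected but not assured by any failure rule.

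Nor does the protocol say that an early EOT counts as week 25. The point is only that nothing in it prevents this. Visit windows are ordinary SAP content; the shared visit label is fixed here.

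**Conclusion.** The point holds for the supportive PP analysis and for any observed-case summary of the four week-25 endpoints. The routing and the bar on PP imputation are both in the protocol, and a SAP cannot recover a sample that was never scheduled. Sections 8.6.4 and 8.7.4.2 also disagree: the second says PP differs from the primary analysis only in population, while the first imputes for one and not the other.

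The size depends on failure and discontinuation rates that the protocol does not give. Under the assumed splits the overstatement is 11 to 60 points, and its direction is the same on both readings.

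Severity is moderate. The week-1 primary endpoint is untouched, and these are descriptive secondary endpoints in a single-arm study.

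**What to change.** 1. In sections 8.2.2 and 8.6.4, state that a subject who meets treatment failure or stops PRO 140 before week 25 stays in the denominator and counts as not below 400 and not below 50, in PP as well as ITT.
2. In sections 4.3 and 4.3.3, label the visit after an early stop as early termination, separate from EOT, and take week-25 values only from a fixed day window counted from T1.
3. Label the observed mean RNA and CD4 changes as describing non-failures on PRO 140, and add a supportive summary that includes the TF-visit values of failures.
4. Reconcile the week 24, week 25 and T25 wording of the 400-copy criterion in the synopsis and sections 4, 4.3.4 and 5.2.1 with a schedule that draws no RNA at T25.

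The cost is wording and one eCRF visit label, with no new sample. The PP percentages will look less favourable. Failures will still have no measured week-25 value, which is why the counting rule has to be explicit.

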4.3.4 Treatment Failure (TF) Visit

Treatment failure is defined in terms of virologic non-response and virologic rebound in Part 2 of the Treatment Phase:

(1) Virologic non-response is defined as two consecutive viral load results of:

- $<0.5 \log_{10}$ copies/mL decrease in HIV-1 RNA at Day 7 of Treatment Phase Part 2. *[Assessment Timepoint: T3 visit]*
- $<1 \log_{10}$ copies/mL decrease in HIV-1 RNA at or after Week 4 of Treatment Phase Part 2 unless HIV-1 RNA <400 copies/mL. *[Assessment Timepoint: from T6 up to T25 visit]*
- Confirmed plasma HIV-1 RNA levels ≥ 400 copies/mL at Week 24 of Treatment Phase Part 2. *[Assessment Timepoint: T25 visit]*

(2) Virologic rebound is defined as two consecutive viral load results of:

$\geq 1.0 \log_{10}$ copies/mL increase in plasma HIV-1 RNA above nadir level* in Treatment Phase Part 2 *[Assessment Timepoint: from T3 up to T25 visit]* or

*Note: This refers to “Nadir” level in Treatment Phase Part 2 which starts from T2 visit.

- ≥ 400 copies/mL after suppression to <50 copies/mL in Treatment Phase Part 2. *[Assessment Timepoint: from T3 up to T25 visit]*

The following assessments will be performed for subjects who experience treatment failure at any time during the Treatment Phase:

- Assess for any Adverse Events and changes in Concomitant medications (see [section 9](#) and [7.5](#)),
- Complete Physical Examination (see [section 7.7](#)),
- Vital Signs (see [section 7.10](#)),
- Neurological Assessment (see [section 7.9](#)),
- Subject-perceived Injection Site Pain Assessment (see [section 7.14](#)),
- Collection of Blood Specimens (see [section 7.11](#)) for
 - Plasma HIV-1 RNA level
 - TruCount T Assay
 - Complete Blood Count
 - Biochemistry
 - HIV Drug Resistance Assay
 - HIV PhenoSense Entry® Assay
 - HIV Trofile® Assay

- Anti-idiotypic antibodies to PRO 140
- PK sample for PRO 140
- Serum Conc. of ART drugs
- Blood sample collection for Exploratory/Confirmatory analysis
- Change in Optimized Background Therapy based on genotypic and phenotypic results obtained at TF visit.

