As shown in Table 0-2, after 7 days all subjects will enter the 24-week treatment period. During this period, all subjects will receive PRO 140 SC injection and Optimized Background Therapy. Optimized Background Therapy (OBT) is a standard-of-care regimen comprised of 3 or more antiretroviral agents selected by the investigator based on treatment history and genotypic and/or phenotypic assessments.

Table 0-2: 24-week treatment period [PRO 140 + OBT]

Study Drug	Dosage Form	IP concentration	Dosing Frequency and Amount	Route of Administration
PRO 140	Parenteral solution	175 mg/mL	2 injections of PRO 140 (2 X 2 mL/inj.) per week for up to 24 weeks (T2 – T25)	SC injection

Study participants will be regularly monitored for viral load following initiation of PRO 140, and will cease weekly study treatment injections should they experience treatment failure.

Subjects who experience treatment failure at any point during the Treatment Phase will undergo the Treatment Failure (TF) Visit assessments and then return in 4 weeks (\pm allowed window) for the Safety Follow-up Visit.

Treatment failure is defined in terms of virologic non-response and virologic rebound in the Open-Label Treatment Phase of the study.

(1) *Virologic non-response is defined as two consecutive viral load results of:*

- $< 0.5 \log_{10}$ copies/mL decrease in HIV-1 RNA at Day 7 of Treatment Phase Part 2. [Assessment Timepoint: T3 and T4 visit]
- $< 1.0 \log_{10}$ copies/mL decrease in HIV-1 RNA at or after Week 4 of Treatment Phase Part 2 unless HIV-1 RNA < 400 copies/mL [Assessment Timepoint: from T6 up to T25 visit].
- *Confirmed plasma HIV-1 RNA levels ≥ 400 copies/mL at Week 25 of Treatment Phase Part 2. [Assessment Timepoint: T25 visit]*

(2) *Virologic rebound is defined as two consecutive viral load results of:*

- $\geq 1.0 \log_{10}$ copies/mL increase in plasma HIV-1 RNA above nadir level* in Treatment Phase Part 2 [Assessment Timepoint: from T3 up to T25 visit] or

**Note: This refers to "Nadir" level in the Treatment Phase which starts from T2 visit*

Name of Sponsor: CytoDyn, Inc.	
Name of Study Product: PRO 140 (Humanized monoclonal antibody to CCR5)	
Protocol Number: PRO 140_CD02_OpenLabel	Therapeutic Indication: Human Immunodeficiency Virus Type-1 (HIV-1) Infection

 • ≥ 400 copies/mL after suppression to < 50 copies/mL in Treatment Phase Part 2. [Assessment Timepoint: from T3 up to T25 visit] 	

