4 STUDY SCHEDULE

As shown in [Figure 4-1](#), this study is divided into three phases: Screening, Treatment and Follow-up.

Figure 4-1: Study Schematic

(1) **Screening Phase:** This phase lasts up to 6 weeks, consists of Screening Visit (SV) and begins with signing of Informed Consent. Assessments performed during this phase determine the subject's final eligibility for study participation. First treatment will be administered within 42 days of Screening Visit.

All subjects will continue taking their existing ART (failed regimen) during the Screening Phase and first week of the Treatment Phase (Part 1).

(2) **Baseline:** The Baseline (T0) visit will take place within 6 weeks of the Screening Visit, as soon as HIV-1 viral tropism, genotypic and/or phenotypic resistance results are available for review by Investigator. HIV RNA and TruCount Assay will be performed to ensure continued eligibility prior to the first Treatment Visit (T1).

(3) **Treatment Phase:** Subjects will receive up to 25 treatments, given approximately every week (window period of ± 3 days) or until treatment failure is experienced, whichever comes first.

The first Treatment Visit (T1) will take place within one week of the T0 visit.

The injectable study treatment (PRO 140) will be administered by a qualified medical

professional (MD, DO, PA, LPN, LVN, NP, RN, or CMA if permitted by state law) or self-administered by subjects.

Note: *Study treatment injections at T1, T2, T3, T7, T11, T15, T19 and T23 must be administered at clinic. The remaining study treatment injections may be self-administered by subjects outside the clinic.*

Any time during Treatment Period Part 2, if treatment failure occurs, Investigator will readjust antiretroviral regimen based on HIV-1 genotypic and/or phenotypic drug resistance results obtained during the TF visit.

Subjects will be allowed to continue PRO 140 with existing OBT regimen while waiting for new regimen to be constructed by the Investigator.

Treatment failure is defined in terms of virologic non-response and virologic rebound in Part 2 of the Treatment Phase of the study:

a) Virologic non-response is defined as two consecutive viral load results of:

- $<0.5 \log_{10}$ copies/mL decrease in HIV-1 RNA at Day 7 of Treatment Period Part 2. *[Assessment Timepoint: T3 visit]*

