4.2 BASELINE

The Baseline (T0) visit will be performed for subjects who have met all eligibility criteria within 6 weeks of the Screening Visit, as soon as HIV-1 viral tropism, genotypic and/or phenotypic resistance results are available for review by Investigator. HIV RNA and TruCount Assay will be performed to ensure continued eligibility prior to the first Treatment Visit (T1). Subjects who have an HIV RNA result >400 copies/mL will be enrolled at the T1 visit. Subjects who have an HIV RNA result <400 copies/mL will be designated as screen failure.

The following assessments will be performed at the T0 visit:

- Change in concomitant medications (see [section 7.5](#))
- Collection of Blood Specimens (see [section 7.11](#)) for
 - Plasma HIV-1 RNA level
 - TruCount T Assay

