5.2.1 Discontinuation of Study Treatment

Discontinuation of study treatment (PRO 140) and continuation of HAART as per standard of care is recommended if:

- Subject experiences treatment failure

Defined in terms of virologic non-response and virologic rebound in the Open-Label Treatment Phase (Part 2) of the study:

(1) Virologic non-response is defined as two consecutive viral load results of:

- $<0.5 \log_{10}$ copies/mL decrease in HIV-1 RNA at Day 7 of Treatment Phase Part 2. [Assessment Timepoint: T3 visit]
- $<1 \log_{10}$ copies/mL decrease in HIV-1 RNA at or after Week 4 of Treatment Phase Part 2 unless HIV-1 RNA <400 copies/mL. [Assessment Timepoint: from T6 up to T25 visit]
- Confirmed plasma HIV-1 RNA levels ≥ 400 copies/mL at Week 24 of Treatment Phase Part 2. [Assessment Timepoint: T25 visit]

(2) Virologic rebound is defined as two consecutive viral load results of:

- $\geq 1.0 \log_{10}$ copies/mL increase in plasma HIV-1 RNA above nadir level* in Treatment Phase Part 2 [Assessment Timepoint: from T3 up to T25 visit] or

**Note: This refers to “Nadir” level in Treatment Phase Part 2 which starts from T2 visit*

- ≥ 400 copies/mL after suppression to <50 copies/mL in Treatment Phase Part 2. [Assessment Timepoint: from T3 up to T25 visit]

Note: Subjects will be allowed to continue PRO 140 with existing OBT regimen while waiting for new regimen to be constructed by the Investigator.

- Develops AIDS-defining conditions as specified in Appendix I ([Section 16.1](#)) under which subject is unable to continue treatment with study drug (PRO 140), or subject require treatment with prohibited concomitant medications.
- Shows signs or symptoms of clinically significant immunosuppression
- Subject or the subject's clinician wishes to adjust OBT (except in the event of toxicity management).
- Subject becomes pregnant.

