7.11.7 Plasma HIV-1 RNA level and TruCount T Assay

- Frequency of testing: At SV, Treatment Visits 1, 2, 3, 7, 11, 15, 19 and 23, as well as EOT and TF visits. In addition, blood sample will also be collected at all Treatment Failure Follow-up (TF-FU) Visits or Non-Treatment Failure Follow-up (NTF-FU) Visits.
- To assess antiretroviral therapeutic response to PRO 140

Note: *Plasma HIV-1 RNA level will be measured using Human Immunodeficiency Virus 1 (HIV-1), Quantitative, RNA (Abbott RealTime) test.*

TruCount T Assay includes measurement of Absolute Lymphocytes, CD3 cell count, CD4 cell count, CD8 cell count, CD3%, CD4% and CD8%

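### The Day-7 non-response criterion lacks the below-400 copies/mL exemption of the Week-4 criterion, so a low-baseline subject with two small early decreases and an extra RNA sample can be labelled a treatment failure at values accepted later

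*Protocol*

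**What the plan says.** The treatment-failure rule appears four times in the Protocol: in the synopsis, section 4, section 4.3.4 and section 5.2.1. Each time, non-response requires two consecutive results.

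- **Day-7 criterion.** In section 4.3.4 this is less than 0.5 log10 "copies/mL decrease in HIV-1 RNA at Day 7 of Treatment Phase Part 2", with no exemption. Section 4 has the same criterion: "copies/mL decrease in HIV-1 RNA at Day 7 of Treatment Period Part 2". Section 5.2.1 ties it to one visit: "copies/mL decrease in HIV-1 RNA at Day 7 of Treatment Phase Part 2. [Assessment Timepoint: T3 visit". The synopsis names two: "copies/mL decrease in HIV-1 RNA at Day 7 of Treatment Phase Part 2. [Assessment Timepoint: T3 and T4 visit".
- **Week-4 criterion.** In section 4.3.4 this is less than 1 log10 "copies/mL decrease in HIV-1 RNA at or after Week 4 of Treatment Phase Part 2 unless HIV-1 RNA" is below 400 copies/mL. It applies from T6 to T25. The other three statements carry the same exemption.
- **T25 criterion.** Failure is a confirmed value of 400 copies/mL or more.

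Entry is open to low viral loads. Screening requires 400 copies/mL or more (section 3.3.1), and section 4.2 says: "Subjects who have an HIV RNA result >400 copies/mL will be enrolled at the T1 visit".

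Section 7.11.7 schedules HIV-1 RNA as follows: "At SV, Treatment Visits 1, 2, 3, 7, 11, 15, 19 and 23, as well as EOT and TF visits". Section 4.3 also allows extra RNA draws between clinic visits at the investigator's discretion.

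**The concern.** The rule is built to ask less early (0.5 log10) and more later (1 log10). For subjects who enter just above 400 copies/mL it does the reverse. At Day 7 they must show a 0.5 log10 fall, whereas from Week 4, and again at T25, it is enough to be below 400.

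A subject confirmed below 400 soon after T3, but with a fall of less than 0.5 log10 on both results, would therefore be classed as a treatment failure at a level the rule later accepts. Section 3 says injections cease on treatment failure, and section 4.3.4 lists a change of optimized background therapy (OBT) at the treatment-failure visit. These subjects have multi-class resistance or limited options, so losing an agent or changing a regimen needlessly matters to the individual.

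**Working it through.** The Protocol gives no calculated figure on this point, so there is nothing to reproduce. The check is log10 arithmetic on the thresholds.

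**Inputs**
- Day-7 threshold: decrease below 0.5 log10, no exemption (section 4.3.4).
- Week-4 threshold: decrease below 1 log10, exempt if below 400 copies/mL (section 4.3.4).
- Entry: above 400 copies/mL at T0 (section 4.2).
- Reference for the decrease: not named in the criterion; baseline B is assumed.

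**Which values are caught.** A result V fails at Day 7 if log10(B/V) < 0.5, that is, if V > B/10^0.5 = B/3.162. It is also below 400 if V < 400. The affected band is therefore B/3.162 < V < 400. It exists only if B < 400 × 3.162 = 1,265 copies/mL.

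| Baseline B | B/3.162 | Results below 400 that still fail Day 7 | Band width, log10(400 ÷ (B/3.162)) |
|---|---|---|---|
| 401 | 126.8 | 127–399 | 0.50 |
| 600 | 189.7 | 190–399 | 0.32 |
| 800 | 253.0 | 253–399 | 0.20 |
| 1,000 | 316.2 | 317–399 | 0.10 |
| 1,200 | 379.5 | 380–399 | 0.02 |
| 1,265 or more | 400 or more | none | none |

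**Examples**
- Baseline 600, results 250 and 220: log10(600/250) = 0.380 and log10(600/220) = 0.436. Both are below 0.5, so this is failure at Day 7. Both values are below 400, so they are exempt from Week 4.
- Baseline 1,000, result 350: log10(1,000/350) = 0.456, caught if confirmed by a second result in the band.
- Baseline 1,000, result 300: log10(1,000/300) = 0.523, not caught.

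**When a second result can arise.** Part 2 starts at T2, so T3 is its Day 7 and T6 its Week 4. After T3 the next scheduled RNA is T7, four weekly visits later. T7 falls in the T6–T25 range of the Week-4 criterion, where values below 400 are exempt. A second result counted at Day 7 must therefore come from T4, which only the synopsis names and for which no RNA is scheduled, or from a discretionary draw.

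**With the exemption added.** The band B/3.162 to 400 becomes empty. Subjects at or above 400 with a decrease under 0.5 log10 remain failures.

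**The case against.** The strongest reply is that the difference may be deliberate. From a baseline of 401, a 1 log10 fall means about 40 copies/mL (401/10), under the 50 copies/mL that section 3.3.1 uses for detectable virus. The Week-4 criterion thus needs an exemption to be attainable. A 0.5 log10 fall from 401 means 127, which is measurable. This is a reasonable inference, but the Protocol does not state it, and it does not explain why a value accepted at Week 4 should be a failure three weeks earlier.

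A second reply is that the exemption would pass a true non-responder, such as 401 falling to 399 twice. That is so, but the Week-4 criterion already accepts 399. What stands is a small loss in the early check.

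A third is that the scheduled visits do not produce the case. This stands and limits the point. Removing T4 from the synopsis would close one route but leave the discretionary draw. Whether such a draw counts under a criterion that the body text ties to T3 is itself open to interpretation.

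Finally, the consequences are softened elsewhere. Section 5.2.1 only recommends stopping and allows PRO 140 to continue while a new regimen is built. Section 4.3 lets OBT be continued or adjusted. Section 5.2.2 asks investigators to contact the medical monitor first. The OBT change is to rest on resistance results from the failure visit, yet section 7.11.9 describes the PhenoSense GT assay for 500 copies/mL or more. An OBT change below 400 is therefore not automatic, and if one is made its guidance may be thin, although Table 4-1 also lists an archive test. All this limits the harm; it does not make the definition consistent.

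**Conclusion.** The inconsistency is real and stands in all four statements of the rule, but it is minor. It rests on the decrease being measured from baseline. If another reference were meant, the 1,265 ceiling would apply to that value instead. It also needs a second early sample that is counted at Day 7.

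Three stronger readings are tempting and are not supported:

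- **Every low-baseline subject confirmed below 400 soon after T3 is a failure.** Both results must also show less than 0.5 log10 decrease, and the band narrows quickly as baseline rises.
- **The planned schedule generates these failures.** It does not, because no RNA is scheduled between T3 and T7.
- **The efficacy results are compromised.** The primary endpoint is read at the end of Part 1, before the rule applies, and sections 8.2.1 and 8.2.2 define no endpoint by treatment failure. A wrongly labelled subject would leave the usual visit path, and each subject is 1 of up to 25 planned. Section 5.2.2, however, asks that such subjects be followed where possible.

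The Protocol gives no baseline RNA distribution and no rate of extra draws, so the number affected cannot be estimated. It is likely small and could be zero. What remains is a wrong label and a possible needless treatment change in a rare subject.

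**What to change.** Add the Week-4 criterion's exemption for HIV-1 RNA below 400 copies/mL to the Day-7 non-response criterion in the synopsis and in sections 4, 4.3.4 and 5.2.1. Leave the other criteria as they are.

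No visit or sample is added. The change alters a stopping rule while subjects are enrolled, so it needs a protocol amendment with IRB approval (section 11.3), and earlier and later subjects would fall under slightly different rules. A few low-baseline slow responders or non-responders below 400 would stay on treatment until the T7 check, four weeks after T3. Discretionary draws remain available in the meantime.
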